## Fitbit Plus Technology Measures

**Wireless Blood Pressure Monitor.** The Omron 10 wireless Bluetooth home BP monitor (Model BP786N) is clinically validated for accuracy according to international guidelines (*Omron: Why validation is important*, 2019). Participants were trained to measure their BP two times per day (morning and night) after they had been seated for at least five minutes with feet flat on the floor and back supported. The easy-wrap ComFit cuff (fits standard to large arms, 9 to 17 inches in circumference) was placed directly on the bare skin of the left upper arm  $\frac{1}{2}$  inch above the elbow with the air tube on the inside of the arm and aligned with the middle finger (Omron Healthcare, 2015b). Three consecutive BP measures were automatically taken with the left arm supported at heart level with one minute between measurements (Whelton et al., 2017). Omron home BP monitors are designed for use on the left arm because validation during clinical studies used the left arm (*FAQs: Blood Pressure Monitors*, 2020). All BP readings were recorded, analyzed, automatically averaged, and synchronized to the Omron Connect app on smartphones. However, real-time tracking in the Fitbit Plus dashboard only occurred for iPhone users. Because Android phones did not automatically transmit Omron BP data to Fitbit Plus,

Android users manually recorded their daily BP measurements in Fitbit Plus and emailed BP recordings weekly from the Omron app generated spreadsheet to the PI to ensure accuracy of BP entries. This study examined changes in BP over time.

**Medication Adherence.** All medications were physically inspected by the PI during baseline data collection. Only prescribed anti-hypertensive medication names, dosages, and time frequencies were recorded in the Fitbit Plus dashboard and updated if changes occurred during the study. In the Fitbit Plus app, each participant manually checked each time they took their BP medicine. The Fitbit Plus dashboard recorded medication-taking and tracked self-reported adherence. This study examined changes in the calculated value of average adherence based on the participant's self-report (Lagasse, 2018, September 19).

**Physical Activity tracker.** Fitbit Inspire HR (Diaz et al., 2015; *Fitbit Inspire and Inspire HR*, 2019) is a physical activity tracker and accelerometer that measures steps, distance, calories burned, and active minutes. The Fitbit was worn on the non-dominant wrist to monitor physical activity during waking hours. Steps in the Fitbit app were synchronized to the Fitbit Plus dashboard. The outcome of interest for this study was changes in the number of steps.

**MyFitnessPal Food Diary.** MyFitnessPal app is used with smartphones to log food intake using a comprehensive food database (Van Horn et al., 2016). MyFitnessPal calculates calories, macronutrients (such as carbohydrates, fats, proteins), and micronutrients (such as vitamins, and minerals) from the food intake. Caloric and sodium intake were synchronized to the Fitbit Plus dashboard. Because sodium is known to increase BP, it was monitored to provide insight to the participant's dietary patterns. Participants were instructed to log their food intake immediately after eating. The outcome of interest in this study was changes in caloric intake.

**Weight Scale.** The Fitbit Aria 2 weight scale (Wi-Fi Smart Scale) was used to measure weight, BMI, and body fat percentage. Participants were instructed to weigh every morning after emptying their bladder. Weight measurements were synchronized via the Fitbit app to the Fitbit Plus dashboard. This study examined changes in body weight.

## Fitbit Monitoring

With smart monitoring of connected devices in Fitbit Plus, data were tracked, analyzed, and transparently displayed to provide opportunities for participants to better understand their condition and self-manage by being actively engaged in their own care. In the CDSMP, all participants were taught to write action plans and report if they were successful, partially successful, or not successful in achieving their plan based on participant self-tracking of their data. Fitbit Plus allowed real-time adherence tracking. If participants were adhering to their action plan, study measures displayed a green color indicating a positive trend and if they were not adhering, measures would display a red color indicating a negative trend, alerting the PI to communicate with participants and encourage active engagement in their self-care.

Only the treatment arm action plans were monitored with individualized coaching messages (ITEC) via secure text messaging in the Fitbit Plus dashboard with real-time participant feedback. Coaching messages focused on helping participant's problem-solve barriers to goal

achievement with relevant dialogue to encourage BP control, medication adherence, and lifestyle modifications (physical activity, caloric intake, and weight management). The PI sent tailored ITEC messages via Fitbit Plus to treatment arm participants weekly for months 1-3, biweekly for months 4-6, and no ITEC messages for months 7-9 (to assess for sustainability).

During months 1-3, the control arm received usual care only, along with monthly manual BP and weight measures. After that time, the control arm was given the same wireless tools and apps as the treatment arm. In addition, they received individualized instruction equivalent to the treatment arm and practiced using the tools during a two-week trial period. For months 4-9, the control arm was monitored with IT via Fitbit Plus with no coaching. Fitbit Plus was used only to track participants for comparative data with the treatment arm. The control participants were not contacted between data collection periods, except to send reminders if they were not participating in daily measures.

All baseline manual measurements and study questionnaires were repeated at 3, 6, and 9 months. All other data were collected through the Fitbit Plus Platform via wireless tools. Personal contact every three months for about 30 minutes provided a human element to the Fitbit Plus technology component and allowed the PI to troubleshoot any problem areas or equipment issues.

Gift cards were given to participants for time expended for baseline assessment (\$20) and repeated measures at 3- (\$30), 6- (\$40), and 9-months (\$60) totaling \$150.

If study participants completed all parts of the research study, then as a completion bonus, they were allowed to keep all measurement tools including the blood pressure monitor, Fitbit, and weight scale, along with the CDSMP book at the conclusion of the study. After Fitbit Plus access ended, participants were able to continue to monitor themselves through the corresponding apps on their smartphone. For those study participants who do not complete the study, the blood pressure monitor, Fitbit, weight scale, and book were returned to the PI when they exited the study.

At the completion of the study, Fitbit Plus transmitted a copy of all collected data at the request of the PI. Both the PI and study participants instructed Fitbit Plus to delete all study participant data when the study ended.

A summary of the overall results of the project in ‘lay’ language was shared with participants in their preferred format (such as email, letter, or in-person) while ensuring confidentiality of individual responses after the study has ended.

## **Data safety and Monitoring**

The Data Safety and Monitoring Plan (DSMP) ensured the safety of research participants and protection of the integrity and confidentiality of the clinical trial study data. Because this is a small study with low risk, the PI, mentor, and biostatistician provided oversight of this study. The DSMP was reviewed monthly (and more frequently as needed). Progress reports, including participant recruitment, retention/attrition, and adverse events (AEs), were addressed at each of

the monthly reviews. All AEs identified were reported to the Institutional Review Board (IRB) and to the National Heart, Lung, and Blood Institute (NHLBI) as applicable.

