**Hill-Bone Compliance to High Blood Pressure Therapy Scale (Hill-Bone CHPPTS).** The Hill-Bone CHPPTS was designed to assess medication compliance/adherence (Kim et al., 2003). The scale is a 14-item assessment tool is a 14-item tool designed to assess medication compliance/adherence. Of the tools three subscales, this study focused on medication taking, 8-items plus one item that addressed prescription refills totaling 9-items. Responses are scored on a 4-point Likert scale from 1 = none of the time to 4 = all of the time. Scores ranged from 9 to 36 and the minimal score indicated perfect adherence. Cronbach's alpha for the Hill-Bone CHPPTS medication compliance subscale was .77, and the total scale was .75 (Kim et al., 2000).

**Self-Efficacy for Managing Chronic Disease (SEMCD).** The SEMCD is a 6-item scale used to measure perceived ability to manage salient aspects of life with chronic disease such as symptom control, role function, and emotional functioning (Lorig et al., 2001). Responses are scored on a 10-point numeral rating scale (1= not at all confident to 10 = totally confident) with higher values indicating self-efficacy. For the SEMCD, the Cronbach's alpha across eight studies ranged from .88 to .91 (Ritter & Lorig, 2014).

**Healthcare Utilization.** Healthcare Utilization is a 4-item tool used to measure the number of times a health care service is used. Responses are single item numbers and self-reported by participants. Test-retest reliability for Healthcare Utilization ranges from .76 to .97 (Lorig et al., 1996).

**Communication with Healthcare Provider.** Communication with Physicians is a 3-item scale used to monitor changes in the key behaviors taught in the CDSMP with items related to prepared questions, understanding treatment, and personal problems. Responses are recorded on a Likert scale (from 0 = never to 5 = always), scored, and averaged. A higher score indicates better communication with providers. Internal consistency reliability for the Communication with Physicians scale is .73 (Lorig et al., 1996).

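### No adverse-event question is described as asked alike in both arms, and contact with the PI differs in months 1-6, so AE counts by arm can partly reflect contact rather than harm

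*Combined protocol and SAP*

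**What the plan says.** *Data safety and Monitoring* holds all that these documents say about AE handling. It states "All AEs identified were reported to the Institutional Review Board (IRB") and, as applicable, to the NHLBI. It also states: "Progress reports, including participant recruitment, retention/attrition, and adverse events (AEs), were addressed at each of" the monthly reviews. Oversight is by the PI, a mentor and the biostatistician. The section does not say how or when AEs are sought, or that the source of an AE is recorded.

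*Fitbit Monitoring* sets the contact schedule. Coaching of the treatment arm by the PI ran "via secure text messaging in the Fitbit Plus dashboard with real-time participant feedback", on this timetable: "weekly for months 1-3, biweekly for months 4-6, and no ITEC messages for months 7-9". Controls had manual BP and weight taken monthly in months 1-3, then individual device instruction and a two-week trial. After that, "The control participants were not contacted between data collection periods", apart from reminders to women who were not logging. Both arms share the main visits: "All baseline manual measurements and study questionnaires were repeated at 3, 6, and 9 months".

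None of the instruments under *Baseline and Repeated Measures* is an AE question. The nearest is a self-reported count collected in both arms: "Healthcare Utilization is a 4-item tool used to measure the number of times a health care service is used". Its four items are not listed, and no link to the safety review is described.

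**The concern.** When AEs are not actively asked about, a count combines how often events occur with how likely they are to reach the study team. Here the second part differs by arm. The coach is the PI, who also sits on the three-person oversight group, so anything mentioned in coaching reaches the review directly. Suppose an injury interrupts a woman's activity plan in month 5. A coached woman has an obvious occasion to say so, because the messages are about barriers to her goals. A control woman has no scheduled occasion until the month-6 visit.

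Two things are at stake. The monthly review could not tell a harm of coaching, for example from increased activity, from better detection. And any report of AEs by arm would carry the same ambiguity, including false reassurance from a low control count.

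**Working it through.** The documents give no contact count and no AE rate, so there is no stated figure to reproduce.

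**1. Scheduled contacts.** Inputs are from *Fitbit Monitoring*. Each three-month step is taken as 13 weeks, 39 weeks in all.

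| Period | Treatment | Control |
|---|---|---|
| Months 1-3 | 13 weekly messages + 1 visit = 14 | 3 monthly checks, the third being the visit = 3 |
| Months 4-6 | 6 biweekly messages + 1 visit = 7 | 1 visit = 1 |
| Months 7-9 | 1 visit = 1 | 1 visit = 1 |
| Total | 22 | 5 |

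- With 4-week months, treatment is 12 + 6 + 3 = 21. With 7 biweekly messages it is 13 + 7 + 3 = 23. The ratio to control is 21/5 = 4.2 to 23/5 = 4.6.
- Adding one device-instruction session to each arm (the treatment arm had its own at the start) gives 22-24 against 6, a ratio of 3.7 to 4.0.
- After month 3, treatment has 6 or 7 messages + 2 visits = 8-9. Control has 2 visits, or 3 contacts with the instruction session.
- Counting scheduled in-person measurement only, treatment has 3 and control has 5.

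**2. What that could do to AE counts.** Assume equal, constant true event rates, and that an event is recorded only if a contact follows within W weeks. Each contact then covers the smaller of W and the gap since the previous contact. W is an assumption; the documents give no value.

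| W | Treatment weeks covered (months 1-3 + 4-6 + 7-9) | Control weeks covered | Ratio |
|---|---|---|---|
| 2 weeks | 13 + 13 + 2 = 28 of 39 (72%) | 3×2 + 2 + 2 = 10 of 39 (26%) | 2.8 |
| 4 weeks | 13 + 13 + 4 = 30 of 39 (77%) | 3×4 + 4 + 4 = 20 of 39 (51%) | 1.5 |
| 13 weeks | 39 of 39 | 39 of 39 | 1.0 |

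The monthly checks are 13/3 = 4.33 weeks apart, so a 4-week window covers 12 of the first 13 weeks in controls. If the controls' two-week trial also counts as covered, the ratios become 28/12 = 2.3 and 30/22 = 1.4.

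**3. Direction.** The table treats a text message and a visit as equally likely to reveal an event. If only in-person contacts did so, the 2-week row would be 3×2 = 6 against 10 weeks, a ratio of 0.6, and the whole difference would come from months 1-3 (2 against 6 weeks).

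**4. Monthly review.** Of the six reviews in months 4-9, two follow a scheduled control visit, or three if the instruction session falls in month 4. Month 5 is the one month in which controls clearly have no scheduled contact while the treatment arm does. In months 7 and 8 neither arm has any.

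**The case against.** The other side has real weight.

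- **No comparison is planned.** The SAP contains no AE analysis by arm, and AEs serve oversight and reporting. This stands. It limits the point to the monthly review and to any later report by arm.
- **The full Data Safety and Monitoring Plan is only summarised.** It may contain a symmetric AE procedure. If so, citing it settles the matter.
- **The contacts are unlike.** About 19 of the 22 treatment contacts are messages about goals, not health enquiries, and controls are seen in person more often in months 1-3. This stands for direction in that period. It does not make ascertainment equal.
- **The window is arbitrary.** A 13-week recall is plausible for hospital or emergency care and removes the difference. This stands, and the range must include 1.0.
- **The study is small and described as low risk.** That judgement itself depends on events being seen in both arms.
- **The work is reported in the past tense.** This restricts which remedies remain available.

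A reader might infer that the coaching arm will show more AEs, perhaps nearly threefold, or that controls give the review nothing after month 3. The documents support neither. No AE data are shown, and the threefold figure is one end of an assumed range. Controls have device instruction, a trial period monitored by the PI, reminders, daily device data and two visits after month 3, although no safety use of the device data is described.

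**Conclusion.** The point holds in limited form. As documented, AEs are whatever comes to light, and the routes by which they can do so differ by arm in months 1-6: about 22 against 5-6 scheduled contacts overall, and 8-9 against 2-3 after month 3. AE counts by arm can therefore partly reflect the frequency and type of contact. Greater detection with coaching is the likely direction, because the messages are two-way and reach the PI. It is uncertain in months 1-3, and there is no arm difference in scheduled contact in months 7-9.

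With messages and visits weighted equally, the apparent excess with no true difference runs from 1.0 to about 2.8, according to the assumed window. It is likely to be small for serious events that are recalled at the next visit and larger for minor ones. The efficacy analysis is not affected.

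**What to change.** In *Fitbit Monitoring* and *Data safety and Monitoring*:

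1. Ask both arms the same short AE questions, covering events since the last visit, at the existing 3-, 6- and 9-month visits.
2. Record the source of each AE (visit, coaching message, other).
3. Pass relevant Healthcare Utilization counts to the safety review, if the tool has hospital or emergency items.
4. Base any between-arm AE statement on visit-elicited events and Healthcare Utilization counts, and list coaching-sourced AEs separately.

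For data already collected, report Healthcare Utilization by arm, split AEs by source where records allow, and state that ascertainment differed between arms. If the full Data Safety and Monitoring Plan already has a symmetric procedure, cite it instead.

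The cost is a few minutes at visits already made and one REDCap field. The drawback is a three-month recall period for minor events, the same in both arms.

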### Statistical Analysis Plan

**Sample size and power.** All participants meeting study eligibility requirements received the CDSMP classes for 6 weeks. Participants from this pool were randomized to the treatment arm (with ITEC and electronic devices such as the home BP monitoring, weight scale, and physical activity tracker), and the control arm, with IT monitoring only. Our sample of  $n=45$  participants per arm ( $N=90$  in total), measured at baseline, and at 3-, 6-, and 9-months post CDSMP, has approximately 80% power (assuming 5 dropouts per arm) to detect an effect size of  $\sim 0.205$  or greater at the  $\alpha=0.05$  level of statistical significance, given a realistic range of simulated unstructured covariance matrices. Assuming an 11% rate of attrition, the enrollment target was set at 90 for both arms, which would yield a final sample of 80 participants, or 40 per arm.

**Statistical analysis.** A hierarchical, mixed-effects repeated measures design was used to analyze the primary and secondary outcomes of interest. This model, which allows for heterogeneous variances across time points, is preferred over a simple univariate model that requires compound symmetry (i.e., the correlation between a measurement at time  $T_i$  and any other measurement within the same patients at  $T_j$ , is equal for all  $i$  and  $j$ ). A mixed-effects model is more efficient for handling missing at random (MAR) data than, for example, a generalized estimating equations (GEE) repeated measures approach, which requires the more restrictive assumption that missing data are missing completely at random (MCAR). We performed a sensitivity analysis using both a GEE model and sequential application of the EM algorithm to impute missing data. Data from participants ( $n=7$ ) who dropped out of the study before their first post-CDSMP visit were not included in the analysis. However, baseline information for these participants were compared with participants who continued in the study.

When appropriate a constrained longitudinal data analysis (cLDA) model was used, assuming the same baseline mean for treatment and referent arms with missing baseline data. The cLDA model examines treatment differences over time. Coffman et al. (2016) cite the cLDA as the method of choice for longitudinal RCTs because it yields robust estimates of treatment effect differences under reasonable missing data assumptions.

Both models are valid for repeated measures if data are missing at random (MAR). Little's test was used to determine if variables were missing completely at random (MCAR) while significant covariate-dependent missing values were identified by regressing a dichotomous indicator variable for missingness against key models factors. (Li, 2013) That is, if the missing values were non-randomly associated with the latter variables of interest, the mechanism was deemed to be missing at random (MAR). A sampling of observed vs. non-unobserved items were subjectively scrutinized for signs of a 'missing not at random (MNAR)' pattern for the data. Overall, no relevant violation of the MAR assumption was evident in our analyses.

Descriptive statistics were used to summarize demographic data (such as marital status, education, and income) of study participants.

An independent (unpaired) samples t-test was used to determine the difference between the means of the treatment and referent groups. The dependent (paired) sample t-test was used to determine the mean differences between variables (systolic and diastolic BP and weight/BMI) for treatment and referent group participants from baseline (post-CDSMP) to month 3, from month 3 to 6, and from month 6 to 9. Time frames were allotted to further participant engagement in self-management.

The use of a two-sample t-test versus non-parametric methods for nonnormally distributed data has been debated in the literature (le Cessie et al., 2020). In general, the former is reasonable robust to departures from normality, providing that the sample sizes are sufficiently large, and the underlying variances are finite (with no extreme outliers) (Lumley et al., 2002)

All data collection tools (except the Hill-Bone CHBPTS medication subscale) were converted to a 100-point scale to enable comparison. Questionnaire scores were analyzed for changes across several time points using a mixed-effects repeated measures model for both groups. In comparison to a repeated measures ANOVA test, the mixed model tends to yield valid estimates of treatment effects even when the missing values are not completely missing at random (Detry & Ma, 2016). Rounding was based upon significant digits rather than a fixed number of decimal places (i.e., Goldilocks method) (Efird, 2021). Data were analyzed using SAS - v 9.4 (Cary, NC).

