The intervention will be divided into three steps. At Step 1 for 3 months, the treatment arm will receive electronic monitoring (of participants' BP, weight, physical activity, food diary, and medication-taking) with weekly Interactive Technology Enhanced Coaching (ITEC) while the control arm will receive usual care with manual BP measurements monthly. At Step 2 for three months, the treatment arm will receive electronic monitoring with ITEC biweekly, and the control arm will receive electronic monitoring only. At Step 3 for three months, both the treatment arm and the control arm will receive electronic monitoring only.

Information from this study may be used to enhance self-care management, control blood pressure, and increase the quality of life for Black women who are burdened with the adverse effects of HTN and its high disability and mortality rates.

Our sample of n=45 participants per arm (N=90 in total), will be measured (electronic measurements, anthropometric measurements, and data collection tools) at baseline, 3 months, 6

months, and at 9 months post CDSMP. A hierarchical, mixed-effects repeated measures design will be used to analyze the data.

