## **Objective**

The specific aims for this study evaluated the effectiveness of an established Chronic Disease Self-Management Program (CDSMP) plus an interactive technology-enhanced coaching (ITEC) intervention on improving 1) BP control, and 2) medication adherence and lifestyle modifications (physical activity, diet, and weight management) compared to the CDSMP and interactive technology (IT) alone.

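### The stated 80% power is not shown to apply to ITEC versus IT alone, because the two arms have that contrast concurrently only in months 4-6

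*Combined protocol and SAP*

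**What the plan says.** The Objective compares the self-management programme plus ITEC on blood pressure, adherence and lifestyle "compared to the CDSMP and interactive technology (IT) alone". The Design section states the hypothesis in the same terms. The sample size paragraph of the SAP repeats the contrast, giving the treatment arm ITEC and devices "and the control arm, with IT monitoring only". It says that 45 per arm, measured at baseline and at 3, 6 and 9 months, "has approximately 80% power (assuming 5 dropouts per arm) to detect an effect size of" about 0.205 at alpha 0.05. It refers to simulated unstructured covariance matrices but gives no values. It names no model term, visit or metric for the 0.205. On the analysis, it says: "The cLDA model examines treatment differences over time".

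The schedule elsewhere has three steps.

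- **Months 1-3.** Description of the Study says "the control arm will receive usual care with manual BP measurements monthly". Fitbit Monitoring agrees: "During months 1-3, the control arm received usual care only, along with monthly manual BP and weight measures". Control received the devices only after that.
- **Months 4-6.** The treatment arm has devices with biweekly coaching. Control has devices without coaching.
- **Months 7-9.** "At Step 3 for three months, both the treatment arm and the control arm will receive electronic monitoring only". Fitbit Monitoring describes the treatment arm's coaching as stopped: "and no ITEC messages for months 7-9 (to assess for sustainability".

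**The concern.** The aim, the hypothesis and the power paragraph all describe one contrast, ITEC against IT alone, as if it held throughout follow-up. Under the step schedule it holds concurrently in months 4-6 only, and month 6 is the only scheduled visit that closes such a period. Two errors of interpretation are then open.

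- A null month-6 result could be read against 80% power, although nothing in the SAP ties that figure to month 6.
- A positive month-3, averaged or overall arm-by-visit result could be reported as coaching adding to IT, when part or all of it may come from control having no devices in the first three months.

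The SAP does not say which term tests the aim, so nothing in the plan blocks either reading.

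**Working it through.** **Inputs from the SAP:** 40 analysable per arm, four occasions, effect size about 0.205, power about 80%, alpha 0.05. **Assumed, because not given:** two-sided test; equal correlation r between any two occasions, at 0.3, 0.5 or 0.7; unit SD at each visit; complete data; baseline adjustment as in cLDA.

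**1. The plan's own figures.** The attrition arithmetic agrees: 5/45 = 11.1%, and 80/(1 - 0.11) = 89.9, so 90. The 80% cannot be reproduced from the stated inputs, so three readings of 0.205 were tried:

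- (a) a difference of 0.205 SD;
- (b) Cohen's f for a between-arm effect, so d = 2 x 0.205 = 0.41 SD;
- (c) Cohen's f for arm-by-time over four occasions, with equal baselines and a constant follow-up difference, so d = 0.205/sqrt(0.1875/4) = 0.947 SD.

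**2. Formulas.** Power is from the noncentral t with 77 df and noncentrality d/SE.

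- One visit: SE = sqrt(2(1 - r²)/40), which gives 0.213, 0.194 and 0.160 for r = 0.3, 0.5 and 0.7.
- Mean of three follow-up visits: SE = sqrt(2[(1 + 2r)/3 - r²]/40), which gives 0.149, 0.144 and 0.124.

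**3. Results.**

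| Quantity | r = 0.3 | r = 0.5 | r = 0.7 |
|---|---|---|---|
| Three-visit mean, 0.205 SD at every visit | 27.5% | 28.9% | 36.9% |
| Three-visit mean, 0.41 SD at every visit | 77.6% | 80.1% | 90.2% |
| Month 6, reading (a), 0.205 SD | 15.8% | 18.2% | 24.5% |
| Month 6, reading (b), 0.41 SD | 47.5% | 55.2% | 71.7% |
| Month 6, reading (c), 0.947 SD | 99.2% | 99.8% | >99.9% |
| Month 6, difference with 80% power | 0.605 SD | 0.549 SD | 0.453 SD |

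Reading (b), with the same effect at all three visits, comes close to the stated 80%. Under the step schedule, two of those visits do not compare ITEC with IT. Reading (c) fits the stated figure poorly: under compound symmetry the arm-by-time test would have 96.7% power at r = 0.3, and more at higher r. It cannot be excluded for the unstructured matrices actually used. For 0.41 SD to reach 80% at month 6, r would have to be about 0.76 or more.

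**4. The opposite error.** Suppose coaching adds nothing, and devices lower blood pressure by x = 0.3 or 0.5 SD against usual care at month 3 only (assumed).

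- The three-visit mean difference is x/3. At 0.3/3 = 0.10 SD it is significant in 10.2%, 10.5% and 12.5% of trials for the three correlations. At 0.5/3 = 0.167 SD the figures are 19.8%, 20.7% and 26.2%.
- The 3-df test of arm differences over the three visits (F with 3 and 75 df) is significant in 19.7%-39.3% at x = 0.3 and 49.6%-84.8% at x = 0.5.

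**5. Month 6 is not immune.** If the treatment arm's three-month device head start still leaves 0.2 SD at month 6 (assumed), with no coaching effect, the month-6 test is significant in 15.3% (r = 0.3) to 17.5% (r = 0.5). At 0.3 SD the figures are 28.4% to 33.4%.

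**The case against.** The 80% may be correct for whatever term was simulated. That stands: a reader might infer that the sample size calculation is wrong or the trial underpowered, and the documents support neither. They do not say which term, metric or covariances were used. Across the three readings, month-6 power runs from 15.8% to above 99%.

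The two nine-month regimens were randomised, and comparing them is valid. The Design section speaks of differences after the intervention, with measurement over nine months, and power over four occasions fits that reading. This also stands, but it is a comparison of regimens and should carry that name. It is not the contrast that the Objective and the power paragraph describe.

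No arm effect averaged over visits is specified, and the steps are disclosed, with months 7-9 labelled as sustainability. That is fair. The gap is that no term is named as the test of the aim, so step 4 shows a risk and not a planned error.

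A reader might also infer that month 6 gives a clean test of coaching. It does not: by then the treatment arm has had devices for six months and control for about three, and step 5 shows what a residual device effect would do.

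Steps, calories and app-recorded adherence come from devices that control lacked until month 4. The illustration therefore covers the manually measured outcomes, chiefly blood pressure and weight, and not those. Finally, the SAP is written after data collection, so nothing here changes what the trial can detect. It changes what the results may be said to show.

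**Conclusion.** The concern holds in a limited form. The control description in the power paragraph conflicts with the step schedule, and the stated 80% is not shown to apply to ITEC versus IT alone. A month-3 or all-visit difference cannot be read as the effect of coaching over IT. This rests on the documents alone.

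The size at month 6 is only illustrative. With 40 per arm and an assumed baseline correlation of 0.3-0.7, 80% power is reached at about 0.60-0.45 SD. Power is 15.8%-24.5% if 0.205 is an SD difference and 47.5%-71.7% if it is a between-arm Cohen's f. Neither metric is stated. Month 6 is the right place for an ITEC-versus-IT statement only because no other visit closes a concurrent period of that contrast, and the statement carries the head-start confounding with it. The point should be corrected before results are interpreted.

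**What to change.** Reconcile the control-arm description in the sample size paragraph with Description of the Study and Fitbit Monitoring. If the step schedule stands:

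1. Label month 3 as ITEC plus devices versus usual care, month 6 as ITEC versus IT with a three-month earlier device start in the treatment arm, and month 9 as persistence after coaching ended.
2. Base any ITEC-versus-IT statement on the month-6 arm difference from the planned cLDA model. State the head-start confounding and, if it is so, that this contrast was named after data collection.
3. Report any all-visit result as a comparison of the two nine-month regimens, not as ITEC versus IT.
4. Restate the power sentence from the original run, with the model term, metric and covariance values to which 0.205 and 80% belong. Give the month-6 detectable difference separately, with its assumed correlation: about 0.60 SD at 0.3 and 0.45 SD at 0.7.

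The cost is a few sentences in the SAP and matching labels in the results. It needs no new data, no change to the sample size and no new model.
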